5.1. Overall Design

Table GPGG.2. Subject Groups based on Renal Impairment Status

	Classification	eGFR (mL/min/1.73m ²)
Group 1	Control (normal renal function)	≥ 90
Group 2	Mild renal impairment	60-89
Group 3	Moderate renal impairment	30-59
Group 4	Severe renal impairment	15-29 ≤ 30 and not requiring dialysis
Group 5	End-stage renal disease	Requiring dialysis

Abbreviations: eGFR = estimated glomerular filtration rate (as determined by the Modification of Diet in Renal Disease abbreviated equation).

5.4. Scientific Rationale for Study Design

A comprehensive range of renal impairment is necessary to fully characterize the impact of renal impairment on the PK of LY3298176. Subjects undergoing ~~hemodialysis~~ (Group 5) will be included to determine the effect of dialysis on drug removal.

6.1.3. Additional Inclusion Criteria for Subjects with Mild to Severe Renal Impairment or ESRD

[10] Males or females with stable mild to severe renal impairment, assessed by eGFR or with ESRD (having received hemodialysis for at least 3 months).

6.1.4. Additional Inclusion Criteria for Subjects with T2DM and Renal Impairment or ESRD

[13] Have T2DM ~~controlled~~^{treated} with diet or exercise alone or ~~with~~ ^{stable doses of} ~~on~~ metformin ~~and/or~~ ^{insulins} for at least 8 weeks.

[15] Have a hemoglobin A1c (HbA1c) ~~>7.0~~^{6.0}₀% and ~~<=11.0~~ at the screening visit.

6.2.3. Additional Exclusion Criteria for Subjects with T2DM and Renal Impairment or ESRD

[46] Have taken any glucose-lowering medications other than metformin ~~and/or insulins~~ (refer to Inclusion Criterion [13]), ~~including insulin~~, in the past 3 months before screening. In general, stable dosages of metformin and insulins will be continued; however, a washout period or dose modifications may be necessary to allow for optimal blood glucose monitoring throughout the dosing period at the discretion of the investigator.

7.7. Concomitant Therapy

Stable single oral doses of metformin ~~and/or stable doses of insulins~~ (for at least 8 weeks) are allowed for subjects with T2DM. Refer to Exclusion Criterion [46] in Section 6.2.3. Additional concomitant medications for treatment of T2DM, other than metformin, are not permitted during the study.

Table GPGG.3. Renal Function Classification for Primary Analyses

Group	Classification	eGFR (mL/min/1.73 m ²) ^a	CLcr (mL/min) ^b
1	Control (normal renal function)	≥90	≥90
2	Mild renal impairment	60-89	60-89
3	Moderate renal impairment	30-59	30-59
4	Severe renal impairment	15-29 ^{<30, not requiring} dialysis	15-29 ^{<30, not requiring} dialysis
5	End-stage renal disease	Requiring dialysis	Requiring dialysis

Abbreviations: CLcr = creatinine clearance; eGFR = estimated glomerular filtration rate.

^a Per enrollment classification; eGFR will be calculated using the Modification of Diet in Renal Disease abbreviated equation.

^b CLcr will be calculated using the Cockcroft-Gault formula (Cockcroft and Gault 1976).

Leo Document ID = a4c382cc-21ac-4798-a6a3-c1f096dfe2d1

Approver: PPD

Approval Date & Time: 03-May-2019 14:26:52 GMT

Signature meaning: Approved

Approver: PPD

Approval Date & Time: 03-May-2019 15:03:22 GMT

Signature meaning: Approved

2. ABBREVIATIONS

Abbreviations pertain to the Statistical Analysis Plan (SAP) only (not the tables, figures and listings [TFLs]).

%AUC(t _{last} -∞)	percentage of AUC(0-∞) extrapolated
AE	adverse event
ADA	antidrug antibodies
AUC	area under the concentration versus time curve
AUC(0-∞)	area under the concentration versus time curve from time zero to infinity
AUC(0-t _{last})	area under the concentration versus time curve from time zero to time t, where t is the last time point with a measurable concentration
BMI	body mass index
BQL	below the lower limit of quantification
CL/F	apparent total body clearance of drug calculated after extravascular administration
C _{last}	last quantifiable drug concentration
CLcr	creatinine clearance
C _{max}	maximum observed drug concentration
CRF	Case Report Form
CRU	Clinical Research Unit
CSR	Clinical Study Report
CV	coefficient of variation
e.g.	for example (Latin: exempli gratia)
EC	Early Clinical
ECG	electrocardiogram
eGFR	estimated glomerular filtration rate
ESRD	end-stage renal disease
ICH	International Council on Harmonisation
LLOQ	lower limit of quantification
MedDRA	Medical Dictionary for Regulatory Activities
MDRD	Modification of Diet in Renal Disease
PK	Pharmacokinetic(s)

SAP	Statistical Analysis Plan
SC	subcutaneous
SD	standard deviation
T2DM	Type 2 Diabetes Mellitus
TFLs	Tables, Figures, and Listings
$t_{1/2}$	Half-life associated with the terminal rate constant (λ_z) in noncompartmental analysis
t_{max}	time of maximum observed drug concentration
ULN	upper limit of normal
V_{ss}/F	apparent volume of distribution at steady state after extravascular administration
V_z/F	apparent volume of distribution during the terminal phase after extravascular administration
WHO	World Health Organization

3. INTRODUCTION

This SAP has been developed after review of the Clinical Study Protocol (final version dated 15 January 2018).

This SAP describes the planned analysis of the pharmacokinetic (PK) and tolerability data from this study. A detailed description of the planned TFLs to be presented in the clinical study report (CSR) is provided in the accompanying TFL shell document.

The intent of this document is to provide guidance for the statistical and PK analyses of data. In general, the analyses are based on information from the protocol, unless they have been modified by agreement between Eli Lilly and Company and Covance Early Clinical (EC) Biometrics. A limited amount of information concerning this study (e.g., objectives, study design) is given to help the reader's interpretation. This SAP must be signed off prior to first subject administration for this study. When the SAP and TFL shells are agreed upon and finalized, they will serve as the template for this study's CSR.

This SAP supersedes the statistical considerations identified in the protocol; where considerations are substantially different, they will be so identified. If additional analyses are required to supplement the planned analyses described in this SAP, they may be performed and will be identified in the CSR. Any substantial deviations from this SAP will be agreed upon between Eli Lilly and Company and Covance EC Biometrics and identified in the CSR. Any minor deviations from the TFLs may not be documented in the CSR.

This SAP is written with consideration of the recommendations outlined in the International Council on Harmonisation (ICH) E9 Guideline entitled Guidance for Industry: Statistical Principles for Clinical Trials¹ and the ICH E3 Guideline entitled Guidance for Industry: Structure and Content of Clinical Study Reports².

4. STUDY OBJECTIVES

4.1 Primary Objective

- To estimate the PK parameters of LY3298176 in subjects with mild, moderate, or severe renal impairment, and in subjects with end-stage renal disease (ESRD) after a single 5-mg subcutaneous (SC) dose of LY3298176 compared to control subjects with normal renal function.

4.2 Secondary Objective

- To assess the tolerability of LY3298176 in subjects with mild, moderate, or severe renal impairment, and in subjects with ESRD after a single 5-mg SC dose of LY3298176 compared to control subjects with normal renal function.

4.3 Exploratory Objective

- To evaluate the formation of antidrug antibodies (ADA) to LY3298176 after a single 5-mg SC dose administered to subjects with mild, moderate, or severe renal impairment, and in subjects with ESRD.

5. STUDY DESIGN

This is a Phase 1, parallel-design, open-label, multicenter, single-dose study to assess PK and tolerability of a single dose of LY3298176 in subjects with mild, moderate, or severe renal impairment, or ESRD, and control subjects with normal renal function. Control Group 1 will be healthy subjects with normal renal function. Subjects with Type 2 Diabetes Mellitus (T2DM) will not be included in Group 1. Subjects with T2DM and renal impairment will be permitted to enroll in Groups 2 to 5, whereas subjects with T2DM and normal renal function will not be permitted. Subjects will be assigned to 1 of 5 groups (Groups 1 to 5) based on criteria outlined in [Table 1](#). Estimated glomerular filtration rate (eGFR) will be determined by the Modification of Diet in Renal Disease (MDRD) abbreviated equation using serum creatinine levels obtained at Screening and on Day -1; subjects will be assigned to groups based on values from Day -1.

The control subjects (Group 1) will be selected in order that the mean and distribution of Group 1 are comparable to the mean and distribution for each group with renal impairment (Groups 2 through 5) for age (± 10 years), sex, race, weight (± 10 kg), and body mass index (BMI) ($\pm 20\%$), as far as is practically possible³.

Table 1. Subject Groups based on Renal Impairment Status

	Classification	eGFR (mL/min/1.73m ²)
Group 1	Control (normal renal function)	≥ 90
Group 2	Mild renal impairment	60-89
Group 3	Moderate renal impairment	30-59
Group 4	Severe renal impairment	15-29
Group 5	End-stage renal disease	Requiring dialysis

[figure not shown]
Abbreviations: eGFR = estimated glomerular filtration rate (as determined by the Modification of Diet in Renal Disease abbreviated equation).

[Figure 1](#) and [Figure 2](#) illustrate the study design.

Subjects will visit the Clinical Research Unit (CRU) to sign the informed consent document and undergo screening procedures up to 28 days prior to dosing.

[figure not shown]
Subjects will be admitted to the CRU on Day -1. Subjects will be administered a single dose of LY3298176 on Day 1 and will remain in the CRU until after assessments are completed on Day 5. Subjects will return for study visits on Days 8 and 15 and for a final follow-up visit at least 28 days postdose.

For subjects with ESRD, administration of LY3298176 should occur at least 24 hours prior to the next planned dialysis session. The time and dates of dialysis sessions from the session immediately prior to dose through Day 8 will be recorded in the case report form (CRF). To eliminate potential variation between different types of dialysis membrane, only high-flux polysulfone membranes will be used.

Abbreviations: ADA = antidrug antibodies; D = Day; PK = pharmacokinetic.

Figure 1. Illustration of study design for Groups 1 to 4.

† The first postdose dialysis session should be scheduled to start at least 24 hours after administration of LY3298176. Subsequent dialysis sessions should be scheduled as clinically appropriate.

Abbreviations: ADA = antidrug antibodies; D = Day; PK = pharmacokinetic.

Figure 2. Illustration of study design for Group 5.

6. TREATMENT

The TFLs will include a subheader for treatment (X mg LY3298176 SC) throughout. The following is a list of group abbreviations that will be used in the TFLs.

Group	Order in TFL
Control (normal renal function)	1
Mild renal impairment	2
Moderate renal impairment	3
Severe renal impairment	4
End-stage renal disease	5

7. SAMPLE SIZE JUSTIFICATION

Approximately 58 subjects will be enrolled so that approximately 48 subjects complete the study, such that approximately 8 subjects per group complete Groups 2 through 5. Approximately 16 completers are needed from Group 1 in order to facilitate demographic matching with the subjects in other groups.

The sample size is not selected to satisfy an a priori statistical requirement. However, the sample size (16 subjects for the control group and 8 subjects per group for the other groups) will provide a 90% coverage probability of the half-width of the 90% confidence interval within 0.29 on a log-scale for comparison of each group to the control group for the area under the concentration versus time curve (AUC) or maximum observed drug concentration (C_{max}), assuming the variability (coefficient of variation [CV]) is 32%. In the natural scale, assuming the ratio is r , the 90% confidence interval for the ratio should be within (0.74 r , 1.34 r).

Subjects who are enrolled but not administered treatment may be replaced to ensure that a sufficient number of subjects complete the study.

8. DEFINITION OF ANALYSIS POPULATIONS

The “Safety” population will consist of all enrolled subjects, whether or not they completed all protocol requirements.

The “Pharmacokinetic” population will consist of all subjects who received at least one dose of study drug and have evaluable PK data.

All protocol deviations that occur during the study will be considered for their severity/impact and will be taken into consideration when subjects are assigned to analysis populations.

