5.1. Overall Design

This is a Phase 1, parallel-design, open-label, multicenter, single-dose study to assess PK and tolerability of a single dose of LY3298176 in subjects with mild, moderate, or severe renal impairment, or ESRD, and control subjects with normal renal function. Control Group 1 will be healthy subjects with normal renal function. Subjects with T2DM will not be included in Group 1. Subjects with T2DM and renal impairment will be permitted to enroll in Groups 2 to 5, whereas subjects with T2DM and normal renal function will not be permitted. Subjects will be assigned to 1 of 5 groups (Groups 1 to 5) based on criteria outlined in [Table GPGG.2](#). For description of enrollment order and interim analysis, see Section [10.3.7](#). Estimated glomerular filtration rate (eGFR) will be determined by the Modification of Diet in Renal Disease (MDRD) abbreviated equation ([Appendix 8](#)) using serum creatinine levels obtained at Screening and on Day -1; subjects will be assigned to groups based on values from Day -1. See Sections [5.2](#) and [10.1](#) for sample size information.

The control subjects (Group 1) will be selected in order that the mean and distribution of Group 1 are comparable to the mean and distribution for each group with renal impairment (Groups 2 through 5) for age (± 10 years), sex, race, weight (± 10 kg), and body mass index (BMI) ($\pm 20\%$), as far as is practically possible (additional information will be provided to the investigators in a separate document) (FDA 2010). An effort will be made to enroll control subjects that are representative of the races of the impaired subjects. One-to-one matching of subjects (1 impaired subject matched to 1 healthy subject in 1 or more impairment groups using the same criteria previously described) may be used to facilitate interim analysis.

Table GPGG.2. Subject Groups based on Renal Impairment Status

	Classification	eGFR (mL/min/1.73m ²)
Group 1	Control (normal renal function)	≥ 90
Group 2	Mild renal impairment	60-89
Group 3	Moderate renal impairment	30-59
Group 4	Severe renal impairment	<30 and not requiring dialysis
Group 5	End-stage renal disease	Requiring dialysis

Abbreviations: eGFR = estimated glomerular filtration rate (as determined by the Modification of Diet in Renal Disease abbreviated equation).

[figure not shown]
[Figure GPGG.1](#) and [Figure GPGG.2](#) illustrate the study design.

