10.1. Sample Size Determination

Approximately 58 subjects will be enrolled so that approximately 48 subjects complete the study, such that approximately 8 subjects per group complete Groups 2 through 5. Approximately 16 completers are needed from Group 1 in order to facilitate demographic matching with the subjects in other groups.

The sample size is not selected to satisfy a priori statistical requirement. However, the sample size (16 subjects for the control group and 8 subjects per group for the other groups) will provide a 90% coverage probability of the half-width of the 90% confidence interval within 0.29 on a log-scale for comparison of each group to the control group for AUC or C_{max} . Assuming the variability (coefficient of variation [CV]) is 32%. In the natural scale, assuming the ratio is r , the 90% confidence interval for the ratio should be within (0.74r, 1.34r).

Subjects who are enrolled but not administered treatment may be replaced to ensure that a sufficient number of subjects complete the study.

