10.3. Statistical Analyses

Statistical analysis of this study will be the responsibility of Eli Lilly and Company or its designee.

Pharmacokinetic analyses will be conducted on data from all subjects who receive at least one dose of the IP and have evaluable PK.

Safety analyses will be conducted for all enrolled subjects, whether or not they completed all protocol requirements.

Immunogenicity analyses will be conducted for all subjects who receive at least one dose of IP.

Additional exploratory analyses of the data will be conducted as deemed appropriate. Study results may be pooled with the results of other studies for population PK analysis purposes to avoid issues with post-hoc analyses and incomplete disclosures of analyses.

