Appendix 1. Abbreviations and Definitions

Term	Definition
ADA	antidrug antibodies
AE	adverse event: Any untoward medical occurrence in a patient or clinical investigation subject administered a pharmaceutical product that does not necessarily have a causal relationship with this treatment. An AE can therefore be any unfavorable and unintended sign (including an abnormal laboratory finding), symptom, or disease temporally associated with the use of a medicinal (investigational) product, whether or not related to the medicinal (investigational) product.
ALP	alkaline phosphatase
ALT	alanine aminotransferase
AST	aspartate aminotransferase
AUC	area under the concentration versus time curve
AUC_{0-∞}	area under the concentration versus time curve from time zero to infinity
AUC_{0-t_{last}}	area under the concentration versus time curve from time zero to the time of last measured concentration
BP	blood pressure
BMI	body mass index
CKD-EPI	Chronic Kidney Disease Epidemiology Collaboration
CLcr	creatinine clearance
C_{max}	maximum drug concentration
complaint	A complaint is any written, electronic, or oral communication that alleges deficiencies related to the identity, quality, purity, durability, reliability, safety or effectiveness, or performance of a drug or drug delivery system.
compliance	Adherence to all the study-related requirements, good clinical practice (GCP) requirements, and the applicable regulatory requirements.
confirmation	A process used to confirm that laboratory test results meet the quality requirements defined by the laboratory generating the data and that Lilly is confident that results are accurate. Confirmation will either occur immediately after initial testing or will require that samples be held to be retested at some defined time point, depending on the steps required to obtain confirmed results.
CP	clinical pharmacologist

CRF	case report form
CRP	clinical research physician: Individual responsible for the medical conduct of the study. Responsibilities of the CRP may be performed by a physician, clinical research scientist, global safety physician or other medical officer.
CRU	clinical research unit
CSE	clinically significant event
DPP	dipeptidyl peptidase
ECG	electrocardiogram
eGFR	estimated glomerular filtration rate
enroll	The act of assigning a subject to a treatment. Subjects who are enrolled in the study are those who have been assigned to a treatment.

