9. STATISTICAL METHODOLOGY

9.1 General

Data listings will be provided for all data that is databased. Summary statistics and statistical analysis will only be presented for data where detailed in this SAP. For continuous data, summary statistics will include the arithmetic mean, arithmetic standard deviation (SD), median, min, max, and N; for log-normal data (e.g., the PK parameters: AUCs and C_{max}) the geometric mean and geometric CV% will also be presented. For categorical data, frequency count and percentages will be presented. Data listings will be provided for all subjects up to the point of withdrawal, with any subjects excluded from the relevant population highlighted. Summary statistics and statistical analyses will generally only be performed for subjects included in the relevant analysis population. For the calculation of summary statistics and statistical analysis, unrounded data will be used.

Mean change from baseline is the mean of all individual subject's change-from-baseline values. Each individual change from baseline will be calculated by subtracting the individual subject's baseline value from the value at the timepoint. The individual subject's change-from-baseline values will be used to calculate the mean change from baseline using a SAS procedure such as Proc Univariate.

Data analysis will be performed using SAS[®] Version 9.4 or greater.

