9.4 Safety and Tolerability Assessments

9.4.1 Adverse Events

Where changes in severity of an AE are recorded in the CRF, each separate severity of the AE will be reported in the listings, only the most severe will be used in the summary tables. A pre-existing condition is defined as an AE that starts before the subject has provided written informed consent and is ongoing at consent. A non-treatment-emergent AE is defined as an AE that starts after informed consent but prior to dosing. A treatment-emergent AE is defined as an AE that occurs postdose or is present prior to dosing and becomes more severe postdose.

All AEs will be listed. Treatment-emergent AEs will be summarized by group, severity and relationship to the study drug. The frequency (the number of AEs, the number of subjects experiencing an AE, and the percentage of subjects experiencing an AE) of treatment-emergent AEs will be summarized by group, Medical Dictionary for Regulatory Activities (MedDRA) version 20.1 system organ class and preferred term. The summary and frequency AE tables will

be presented for all causalities and those considered related to the study drug. Any serious AEs will be tabulated.

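### The Safety population counts enrolled subjects who were never dosed, so any such subject dilutes the treatment-emergent AE percentages

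*SAP*

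**What the plan says.** - **Safety set.** SAP 8: the Safety "population will consist of all enrolled subjects, whether or not they completed all protocol requirements". Protocol 10.3: "Safety analyses will be conducted for all enrolled subjects, whether or not they completed all protocol requirements". Neither sets a dosing condition.
- **Meaning of enrolled.** Protocol Appendix 1: "Subjects who are enrolled in the study are those who have been assigned to a treatment".
- **Timing.** Protocol 5.1: "subjects will be assigned to groups based on values from Day -1". Protocol 7.2.1 puts the single dose on the morning of Day 1.
- **Undosed subjects are foreseen.** Protocol 10.1: "Subjects who are enrolled but not administered treatment may be replaced". SAP 7 repeats the provision.
- **TEAE definition.** SAP 9.4.1: "A treatment-emergent AE is defined as an AE that occurs postdose or is present prior to dosing and becomes more severe postdose". The same section reports, by group, the number of events and the number and percentage of subjects affected.
- **Denominator.** SAP 9.1: "Summary statistics and statistical analyses will generally only be performed for subjects included in the relevant analysis population". SAP 9.4.1 names no other denominator.
- **Other analysis sets.** The PK population (SAP 8) and the immunogenicity set (Protocol 10.3) both require at least one dose.

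**The concern.** A TEAE percentage is meant to describe subjects who were exposed to the drug. Under these definitions a subject who is assigned to a renal group but never injected belongs to the Safety population, yet has no postdose period in which a TEAE could arise. The replacement rule makes this worse: the replacement fills the dosed place, while the replaced subject stays enrolled and stays in the denominator.

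Within a group the error runs one way, towards a lower apparent rate, which is the less cautious direction for a safety summary. Tolerability compared with control is the only secondary objective, and adverse events are its endpoint. The impaired groups are planned at half the size of the control group, so the same number of undosed subjects dilutes them more and can distort the comparison between groups as well as the rates.

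**Working it through.** Neither document states a TEAE rate or a number of undosed subjects, so there is no figure of the plan's own to reproduce. The check has a definitional step and an arithmetic step.

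**Step 1: can an undosed subject be in the Safety population?** Enrolment is assignment to a treatment (Protocol Appendix 1). Assignment rests on Day -1 values and dosing follows on Day 1. Protocol 10.1 and SAP 7 both name the category of enrolled but untreated subjects. No text in SAP 8 or Protocol 10.3 removes them. The answer is yes.

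**Step 2: can that subject count in the numerator?** Both limbs of the TEAE definition need a postdose onset or a postdose worsening. The answer is no.

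**Step 3: size of the dilution.** Inputs:
- E = subjects with a TEAE (assumed).
- D = dosed subjects: 8 per impaired group and 16 in control, the planned completer numbers (SAP 7).
- U = undosed subjects: not given, so 1 and 2 are assumed.

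Reported rate = E/(D+U). Rate among dosed subjects = E/D. Ratio of the two = D/(D+U).

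| Group | E/D | U = 1 | U = 2 |
|---|---|---|---|
| Impaired, D = 8 | 2/8 = 25.0% | 2/9 = 22.2% | 2/10 = 20.0% |
| Impaired, D = 8 | 4/8 = 50.0% | 4/9 = 44.4% | 4/10 = 40.0% |
| Impaired, D = 8 | 6/8 = 75.0% | 6/9 = 66.7% | 6/10 = 60.0% |
| Control, D = 16 | 8/16 = 50.0% | 8/17 = 47.1% | 8/18 = 44.4% |

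The factors are 8/9 = 0.889 and 8/10 = 0.800 for an impaired group, and 16/17 = 0.941 and 16/18 = 0.889 for control.

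**Step 4: effect on the comparison (impaired minus control)** when the rate among dosed subjects is 50% in both groups, so that the true difference is zero:
- one undosed subject in the impaired group only: 4/9 - 8/16 = -5.6 points
- one in control only: 4/8 - 8/17 = +2.9 points
- one in each: 4/9 - 8/17 = -2.6 points

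**Scale.** One further subject with an event in a group of 8 moves the rate by 1/8 = 12.5 points. With U = 0 nothing changes, and with E = 0 the rate stays at 0%.

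**The case against.** The strongest reply is that the effect may never occur and that the tables may not be built this way.

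- **Rarity.** Subjects are admitted on Day -1 and dosed the next morning, so the window is about one night. Day -1 chemistry goes to a central laboratory with no stated turnaround, so it is not shown that every assignment precedes dosing. The planned gap of 58 - 48 = 10 non-completers is not said to consist of undosed subjects. All of this stands as a limit on likelihood. It does not remove the category, which both documents name.
- **Room for a dosed-only denominator.** SAP 9.1 says summaries generally follow the population. SAP 8 lets protocol deviations be considered when populations are assigned. SAP 6 puts a treatment and dose subheader on the outputs. The table shells are a separate document and were not available for this check. None of the visible text is an exclusion rule, however, and not being dosed need not be a protocol deviation. A shell should follow the SAP's population definition, not correct it.
- **Limited weight.** Counts of events, counts of affected subjects and listings do not change. SAP 9.4.11 plans no inference for safety. A reader could recompute the rate from the counts and the disposition listing. The one-subject shift of 5.6 points is less than half of what one more affected subject does in a group of 8. This stands, and it keeps the point below the level of a threat to the trial's conclusions.
- **Keeping everyone preserves predose and procedure-related events.** That purpose is already met, because SAP 9.4.1 lists all AEs and defines a non-treatment-emergent category.

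**Conclusion.** The concern holds. As written, the Safety population understates TEAE percentages in a situation that both documents foresee. One undosed subject multiplies the rate by 0.889 in an impaired group with 8 dosed subjects and by 0.941 in a control group with 16. At a 50% rate that is 5.6 and 2.9 percentage points.

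These sizes assume that the planned completer numbers are the dosed numbers, that U is 1 where the documents give no value, and that the tables use the Safety population as their denominator, as SAP 9.1 implies. The wording defect itself is certain; whether it will bite depends on conduct. The primary PK analysis and the interim dose reviews are not affected. This should be corrected, but it does not put the main result at risk.

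**What to change.** In SAP 8 and Protocol 10.3, define the Safety population as all enrolled subjects who received LY3298176, whether or not they completed the protocol. This brings it into line with the PK and immunogenicity sets. State in SAP 9.4.1 that the number of such subjects in the group is the denominator for TEAE percentages. Keep AEs in enrolled but undosed subjects in the listings, marked as outside the Safety population. If the dose is changed after an interim review, it would also help to show the safety summaries by dose received, though the present point does not depend on that.

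The cost is about one sentence in each document and no new data. Under SAP 3 the SAP supersedes the protocol's statistical considerations, so changing the SAP alone would also work; SAP 11, which now reports no changes from the protocol, would then need an entry. The only consequence for results is that reported TEAE percentages may be slightly higher.
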